### 6.3. Missing Data

No imputation of missing data will be made for any of the outcome variables.

For the purpose of assigning treatment-emergent AEs (TEAEs), prior and concomitant medications, and prior and concomitant procedures, the followings rules will be applied for partial or missing start dates:

- If the day is missing, the first day of the given month will be used unless the month and year are the same as the month and year of enrollment, in which case the date of enrollment will be used.
- If the day and month are missing, the 1st of January will be used unless the year is the same as the year of enrollment, in which case the date of enrollment will be used.

- If the whole date is missing, the date of enrollment will be used.

Imputed dates will not be displayed in data listings.

Other dates will not be imputed.

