### 6.2. Key Definitions

A subject is considered 'entered' into the study after the subject has signed the Informed Consent Form (ICF) and a subject number has been assigned.

A subject is considered 'enrolled' after confirmation of participation eligibility and treatment with the investigational product Juvéderm® VOLIFT™ with Lidocaine has occurred during the study.

Study treatment is defined as initial or touch-up treatment with Juvéderm® VOLIFT™ with Lidocaine.

Baseline is defined as the latest assessment prior to any study treatments for each subject.

Study day will be calculated as (date of event or assessment)-(date of first filler treatment)+1 if the event or assessment was on or after the date of the first filler treatment, and as (date of event or assessment)-(date of first filler treatment) if the event or assessment was before the date of the first filler treatment. The day of first filler treatment is Study Day 1 (Visit 1). If a touch-up treatment is administered, Visits 3, 4, and 5 will be 14 days +/- 3 days later than the visit label and window, e.g. the study day for an assessment at Visit 3 (Day 30) could be 44 +/- 10, rather than 30 +/- 7.

End of study is the last clinical visit an enrolled subject has in this study. For subjects who complete this study, the end of study visit will be their Visit 5; for subjects who drop out early, they will be asked to come back for the last clinical visit for end of study data collection.

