##### **7.5.1. Prior Medication**

Prior medication/therapy is defined as those started and stopped by enrolled subjects before the date of first study treatment.

Partial or missing medication start dates will be handled as per Section 6.3.

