### 7.5.3. Procedures

All procedures received by the subject within 30 days before the initial treatment visit and throughout the study, and any procedure received more than 30 days before screening if considered pertinent to the study in the investigator's judgment, will be recorded on the concomitant procedures page of the eCRF.

All prior and concomitant procedures will be listed together for the Screened Set, including date of and reason for the procedure. The listing will flag procedures as prior or concomitant, where a prior procedure took place before the date of first study treatment, and a concomitant procedure took place on or after the date of first treatment. Partial or missing dates will be handled as per Section 6.3.

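### SAP 6.3 can impute a medicine's start after its own recorded stop, so that it cannot count as prior, and undated procedures default to concomitant

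*SAP*

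**What the plan says.** SAP 6.3 governs treatment-emergent adverse events, prior and concomitant medications, and prior and concomitant procedures. Its "rules will be applied for partial or missing start dates", with three cases:

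- Only the day unknown: "the first day of the given month will be used unless the month and year are the same as the month and year of enrollment"; that exception takes the enrollment date.
- Day and month both unknown: "the 1st of January will be used unless the year is the same as the year of enrollment"; that exception likewise takes the enrollment date.
- Nothing known: "If the whole date is missing, the date of enrollment will be used".

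The section closes with "Other dates will not be imputed", and it keeps imputed dates out of the listings.

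SAP 6.2 fixes what enrollment means: "A subject is considered 'enrolled' after confirmation of participation eligibility and treatment with the investigational product" has occurred.

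The classes come from SAP 7.5. For medicines, "Prior medication/therapy is defined as those started and stopped by enrolled subjects before the date of first study treatment"; SAP 7.5.2 calls a medicine concomitant if it was taken on the day of first treatment or later. For procedures, SAP 7.5.3 states that "a concomitant procedure took place on or after the date of first treatment", calls earlier ones prior, and refers incomplete dates to SAP 6.3.

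SAP 9.3 applies the same date rules to adverse events but adds an override: an event is not treatment-emergent where the evidence clearly places it before first treatment. SAP 7.5 has no counterpart.

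**The concern.** SAP 7.5.1 makes the stop date part of the test for prior use, yet SAP 6.3 imputes the start without looking at it. Where the stop is recorded and precedes treatment, the imputed start can contradict a known fact.

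Such records are to be expected. Exclusion criterion 10 provides a 10-day washout for anticoagulants, NSAIDs and similar substances and allows treatment to be delayed for it. SAP 7.5 collects medicines received in the 30 days before initial treatment. Medicines that ended shortly before Day 1 will therefore be in the database, and some may lack a full start date.

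At stake is whether the medication tables separate use before treatment from use during the study. On one reading, a subject who completed a washout is counted as using that drug on study; on the other, the record drops out of both tables. For procedures, the listing could show as concomitant something that was done before the subject was treated.

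**Working it through.** The plan gives no figure to reproduce here, so the check follows the rule through each pattern of missing dates.

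**Inputs**

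- Imputation rule: SAP 6.3. Start dates only; stop dates are neither imputed nor consulted.
- Enrollment date = first treatment date: this follows from SAP 6.2, because a subject is enrolled only once treated.
- Prior: start and stop both before first treatment (SAP 7.5.1). Concomitant: taken on or after that date (SAP 7.5.2).
- Illustrative dates, assumed: treatment and enrollment on 20 June 2019; medicine stopped on 8 June 2019, which is 20 − 8 = 12 days earlier and outside the 10-day washout.

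**Medicines.** In every row the true stop is 8 June, so the medicine should be prior.

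| What is known of the start | Imputed start | Later than stop? | Meets prior test? |
|---|---|---|---|
| Month and year, same as enrollment | 20 June 2019 | Yes, by 12 days | No |
| Year only, same as enrollment | 20 June 2019 | Yes, by 12 days | No |
| Nothing | 20 June 2019 | Yes, by 12 days | No |
| Month and year, an earlier month (May 2019) | 1 May 2019 | No | Yes |
| Year only, an earlier year (2018) | 1 January 2018 | No | Yes |

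Three of the five incomplete patterns fail and two are handled correctly. This counts patterns and says nothing about how common each is. A complete start date (for example 1 June 2019) is classed correctly.

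**Where the three failing patterns go.** They cannot be prior, because the imputed start is not before first treatment. If the program tests the imputed start, they become concomitant, since 20 June is on the treatment day. If it uses the recorded stop, the medicine was not taken on or after 20 June, so it is not concomitant either. The SAP does not say which test applies.

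**Procedures.** There is one date and no stop date:

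- undated, or dated only to the enrollment month and year, or only to the enrollment year: imputed to 20 June, Study Day 1, flagged concomitant;
- May 2019, day missing: 1 May 2019, prior;
- 2018 only: 1 January 2018, prior.

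**Size.** SAP 7.5 uses the Safety Analysis Set as denominator. With 60 treated subjects, one affected subject changes an overall row by 1/60 = 1.7 percentage points, provided that no other record already places that subject in the row.

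**With the correction.** If a known stop caps the imputed start and a medicine shown to have ended before treatment is classed as prior, all 5 of 5 incomplete patterns come out as prior, against 2 of 5 now. A stop-date cap does nothing for procedures, which need their own rule.

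**The case against.** The strongest reply is that the rule is narrower in effect than it first looks, and that sending uncertain records to the on-treatment side is a normal cautious convention.

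Much of this stands. Any incomplete start in an earlier month or year is imputed to a date before treatment. The washout in criterion 10 concerns ongoing regimens, many of which plausibly began in an earlier month or year. A reader might infer that the rule will be triggered often because washout stop dates fall close to treatment. The documents do not support that: the trigger is the month or year of the start, and the stop plays no part.

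It is also fair that SAP 7.5.2 speaks of medicines taken on or after first treatment. A reader might conclude that the concomitant table is bound to show washed-out drugs as used on study. The text does not settle that; literally read, it leaves the medicine in neither class. This changes the description of the fault but does not remove it, because the prior test still fails.

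For procedures, earlier aesthetic procedures are also taken in the medical history with start and stop dates (SAP 7.3). A lower-face filler in an eligible subject must be at least 24 months old under criterion 6, so a known year will be before the enrollment year. Resurfacing need only be 6 months old under criterion 7, so a date known only to the enrollment year remains exposed, as does any procedure without a date.

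A reader might also infer that a false flag would remove a subject from the Per Protocol Set. SAP 5.5 and 5.6 rest membership on the sponsor's review of deviations captured in the trial management system; nothing says that the derived flags enter it. Nor can it be said that listings would hide the reason for a flag. Imputed dates are not displayed, but the medication listing sorts missing and partial dates first, which suggests that recorded dates appear. The shells are redacted, so this cannot be checked.

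The appeal to caution holds where timing is unknown. It does not hold where a recorded stop date already answers the question.

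**Conclusion.** The point holds in a limited form. For start dates that are wholly missing, or partial and matching the enrollment month and year or the enrollment year, SAP 6.3 can place a medicine's start after its recorded stop. The medicine then fails the prior definition and is either counted as concomitant or lost from both tables. Procedures with the same kinds of incomplete date are flagged concomitant by default, and the evidence override in SAP 9.3 reaches adverse events only.

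The consequence is minor. It is confined to the prior and concomitant medication tables and the flags in the medication and procedure listings. It is at most 1.7 points per affected subject in an overall row of 60. The documents give no count of incomplete dates, so no total can be stated. The primary endpoint is not affected, and the study tests no formal hypothesis.

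The conclusion rests on two assumptions: that the enrollment date is the first treatment date, as SAP 6.2 implies, and that programming follows SAP 6.3 as written.

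**What to change.** Add to SAP 6.3 that an imputed start may not be later than a known stop date, and that a medicine whose full or partial stop date shows that it ended before first treatment is classed as prior.

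In SAP 7.5.3, give procedures the kind of override that SAP 9.3 gives adverse events: class a procedure as prior where evidence already in the database clearly places it before first treatment. Examples are a matching medical history entry, or the visit at which it was recorded if that is captured. Name the accepted evidence before database lock so that the flag does not depend on case-by-case judgement.

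Keep the present default wherever timing is truly unknown.

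The cost is a few sentences and a small programming change. Medicines need no new data, since the Protocol's section on concomitant medications and procedures already collects stop dates. For procedures, the sponsor must first check whether the visit of recording is held; SAP 7.5.3 mentions only the date and the reason. If it is not, medical history is the main source, and some undated procedures will stay under the default.

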#### **6.4. Visit Windows**

Not applicable.

#### **6.5. Pooling of Centers**

Not applicable.

#### **6.6. Subgroups**

As males and females may have differing expectations/perceptions of aesthetic improvement, all data will be analyzed by gender separately.

In addition, all baseline and efficacy tables will be presented for the following subgroups:

- Age group - 18 to 29 years, 30 to 45 years, and 46 years upwards.
- Baseline LFS2 score.
- Fitzpatrick skin phototype - I/II, III/IV, and V/VI.
- Investigational site.

## 7. Demographic, Other Baseline Characteristics and Medication

### 7.1. Subject Disposition and Withdrawals

The number of subjects entered and the number and percentage of subjects enrolled, completed and discontinued, together with the reasons for discontinuation will be summarized for the Screened Set. Disposition details and inclusion and exclusion criteria not met will be listed for the Screened Set.

The number and percentage of subjects included in, and reasons for exclusion from, each of the analysis sets will be presented for the Screened Set. Exclusions from analysis sets will be listed for the Screened Set.

No formal statistical testing will be carried out on these data.

### 7.2. Demographic and Other Baseline Characteristics

Subject demographic and baseline characteristic data will be collected at the screening visit. These data include age at informed consent, gender, childbearing potential, and Fitzpatrick skin phototype. The subject's Fitzpatrick skin phototype will be determined at the screening visit using the parameters listed in Table 3.

Table 3 Fitzpatrick Skin Phototype

Skin type	Typical Features	Tanning ability
I	Pale white skin, blue/green eyes, blond/red hair	Always burns, does not tan
II	Fair skin, blue eyes	Burns easily, tans poorly
III	Darker white skin	Tans after initial burn
IV	Light brown skin	Burns minimally, tans easily
V	Brown skin	Rarely burns, tans darkly easily
VI	Dark brown or black skin	Never burns, always tans darkly

Age at informed consent will be summarized using summary statistics for continuous data. Gender, childbearing potential, and Fitzpatrick skin phototype will be summarized using descriptive statistics for categorical data. Demographic and baseline characteristics will be listed for the Screened Set and summarized for the SS, ES and PPS.

No formal statistical testing will be carried out on these data.

### 7.3. Medical History and Concomitant Diseases

Medical history will be obtained from each subject at the screening visit, and include pertinent surgical history and a detailed history of prior aesthetic procedures with start and stop dates, if applicable, as well as any discontinuations due to intolerance or toxicity.

Medical history will be coded using Medical Dictionary for Regulatory Activities (MedDRA) version 21.0 or higher.

Medical history data will be summarized using summary statistics for categorical data for the SS, sorting alphabetically by system organ class (SOC) and preferred term (PT) within SOC.

Medical history data will be listed for the Screened Set, sorting by subject number, date of onset, and date resolved (placing missing and partial dates first), then alphabetically by SOC and PT within SOC.

#### **7.4. Other Baseline Characteristics**

A urine pregnancy test will be performed by urine dipstick for women of childbearing potential at the screening visit and prior to administration of any study treatment (Day 1 and Day 14, if applicable and at retreatment at Month 12). These data will be listed for women of childbearing potential in the Screened Set.

The POLSS at rest will be assessed at the screening visit and prior to administration of any study treatment at Day 1. The POLSS will be listed for the Screened Set.

No formal statistical testing will be carried out on these data.

#### **7.5. Medication**

All medications or treatments (including prescription medications, dietary supplements, over-the-counter medications, and oral herbal preparations) received by the subject within 30 days before the initial treatment visit and throughout the study, and any medications or treatments received more than 30 days before screening considered pertinent to the study in the investigator's judgment, will be recorded on the prior and concomitant medications page of the electronic case report form (eCRF).

The latest version of the World Health Organization (WHO) Drug Dictionary will be used to classify prior and concomitant medications and therapies by therapeutic class and preferred name.

Prior and concomitant medications/therapies will be summarized separately using descriptive statistics for categorical data for the SS. The summary tables will show the frequency and percentage of subjects with at least 1 usage of medication/therapy by therapeutic class and preferred name, sorting by decreasing overall frequency of therapeutic class then alphabetical within therapeutic class by preferred name. Percentages will be calculated using the number of subjects in the SS as the denominator.

All prior and concomitant medications/therapies will be listed together for the Screened Set, including medication/treatment name, dose, and frequency, and sorting by subject number, start date, and stop date (placing missing and partial dates first), then alphabetically by therapeutic class and preferred name within therapeutic class. The listing will flag medications/therapies defined as prior and medications/therapies defined as concomitant.

##### **7.5.1. Prior Medication**

Prior medication/therapy is defined as those started and stopped by enrolled subjects before the date of first study treatment.

Partial or missing medication start dates will be handled as per Section 6.3.

##### **7.5.2. Concomitant Medication**

Concomitant medication/therapy is defined as those taken on or after the date of first treatment.

Partial or missing medication start dates will be handled as per Section 6.3.

### 7.5.3. Procedures

All procedures received by the subject within 30 days before the initial treatment visit and throughout the study, and any procedure received more than 30 days before screening if considered pertinent to the study in the investigator's judgment, will be recorded on the concomitant procedures page of the eCRF.

All prior and concomitant procedures will be listed together for the Screened Set, including date of and reason for the procedure. The listing will flag procedures as prior or concomitant, where a prior procedure took place before the date of first study treatment, and a concomitant procedure took place on or after the date of first treatment. Partial or missing dates will be handled as per Section 6.3.

## 8. Efficacy

Unless stated otherwise, all efficacy analyses will compare post-treatment assessment values to the subject's corresponding baseline assessment value. All efficacy tables will be presented for the subgroups defined in Section 6.6, separately by gender.

### 8.1. Primary Efficacy Endpoint and Analysis

The primary efficacy endpoint is the responder rate for lip fullness on the LFS2, which is defined as the proportion of subjects who show  $\geq 1$ -point improvement on the LFS2 compared to baseline assessment, at Day 30 after last treatment received.

The LFS2 is an Investigator assessment of overall lip fullness measured by a 5-point scale (see Table 4: Lip Fullness Scale 2 (LFS2)). The investigator will use the LFS2 to perform a live assessment of the subject at the visits specified in Table 2, Schedule of Visits and Procedures. Improvement will be calculated as post-treatment LFS2 score – baseline LFS2 score.

The LFS2 score at baseline and at Visits 3, 4, 5, and 6 as well as the improvement from baseline at all post-treatment visits and the responder rate for lip fullness on the LFS2 at Day 30 will be summarized using summary statistics for categorical data for the ES, and also for the PPS as a supportive analysis. LFS2 grades, scores and improvements from baseline will be listed for the FAS.

Table 4 Lip Fullness Scale 2 (LFS2)

Grade	Description	Score
Very Marked	Very significant red lip show, lower lip pout, and upper lip pout	4
Marked	Significant red lip show and lower lip pout	3
Moderate	Moderate red lip show with slight lower lip pout	2
Mild	Some red lip show; no lower lip pout	1
Minimal	Flat or nearly flat contour, minimal red lip show	0

Photographic images will be collected to capture the subject status at the time of the live assessments. Facial photographs will be captured prior to study treatments and immediately after. Additional images will be captured at the Day 30, Month 3, Month 6, Month 12 and any subsequent visits. Images will be used by the investigator and subject for the facial assessments. 3D photographs will also be taken for each subject to aid in facial assessments and measure the volume change in the lips. Photograph collection details will be listed only for the FAS.

### 8.2. Secondary Efficacy Endpoint(s) and Analyses

#### 8.2.1. Oral Commissures Severity Scale (OCSS)

Change from baseline in OCSS will be determined at each post-treatment visit. The OCSS is an investigator assessment measured on a 4-point scale (see Table 5: Oral Commissure Severity Scale (OCSS)). The Investigator will use the OCSS to perform a live assessment of the subject at the visits specified in Table 2, Schedule of Visits and Procedures. Change from baseline in OCSS will be calculated as post-treatment OCSS score – baseline OCSS score.

The OCSS score at baseline and at Visits 3, 4, 5, and 6 as well as the change from baseline scores at all post-treatment visits will be summarized using summary statistics for categorical data for the ES. OCSS grades, scores and changes from baseline will be listed for the FAS.

Table 5 Oral Commissure Severity Scale (OCSS)

Grade	Description	Score
Severe	Very deep and/or long wrinkle or crease; frown at rest	3
Moderate	Moderately deep and/or long wrinkle or crease; downturned corners	2
Mild	Shallow, just perceptible wrinkle or crease; horizontal or slightly downturned corners	1
None	No wrinkle or fold; slight upturned corners	0

Photographic images will be collected to capture the subject status at the time of the live assessments as detailed in Section 8.1.

#### 8.2.2. FACE-Q™ – Satisfaction with Lips Questionnaire

Subject's assessment of satisfaction with treatment of their lips as measured by the change from baseline in the FACE-Q™ Satisfaction with Lips questionnaire at all post-treatment visits. The subject will assess satisfaction using the 10 items on the Satisfaction with Lips questionnaire of the FACE-Q™ (see Protocol Appendix 5). The responses to the items will be combined to create a Rasch transformed scale score that ranges from 0 to 100. Change from baseline in FACE-Q™ scale score will be calculated as post-treatment FACE-Q™ scale score – baseline FACE-Q™ scale score.

The overall scale score at baseline and at Visits 3, 4, 5, and 6 as well as the change from baseline scores at all post-treatment visits will be summarized using summary statistics for continuous data for the ES. FACE-Q™ responses, scale scores and changes from baseline will be listed for the FAS.

